5.2 Missing Data

For the primary endpoint:

Missing values between the measuring time points will be interpolated linearly.

In case of individual termination of study treatment (due to burden of discontinuation symptoms or recurrence), missing data will be imputed as last observation carried forward (LOCF), which should be a conservative approach.

If all values are missing, the result is missing.

For secondary endpoints:

- a) The same approach as for the primary endpoints will be applied, i.e. LOCF.
- b) No imputation of missing values will be conducted. The analysis is based on the FAS.
- c) Patient observations will be censored at the time point where treatment switching is observed, i.e.
 - treatment discontinuation if treatment should be continued
 - treatment intake if it should be discontinuedOther missing data will not be imputed.
- d) No imputation of missing values will be conducted. The analysis is based on the FAS. As sensitivity analysis the analysis will be repeated on multiple imputed data sets.
- e) No imputation of missing values will be conducted. The analysis is based on the FAS. As sensitivity analysis the analysis will be repeated on multiple imputed data sets.
- f) No imputation of missing values will be conducted. The analysis is based on the FAS.

For multiple imputation a fully conditional specification strategy will be used to generate 20 imputations. The results pooled according to Rubin's rule will be reported.

For the primary endpoint and the secondary endpoint a) the analysis based on imputed data (preserving the ITT population) will be primarily reported.

For all other secondary endpoints the analysis based on the FAS will be primarily reported and analyses based in imputed data are sensitivity analyses.

If other imputation methods are necessary for further additional analyses they will be defined in an additional SAP.

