2.1 Trial Design

PHEA is a prospective, randomised, parallel-group, partly blinded, open-hidden discontinuation trial with a 2x2-factorial design. The allocation ratio is 1:1:1:1 for the four groups:

- Treatment discontinuation and high expectation - open discontinuation (OD):
Patients in this group receive gradually decreasing doses of prescribed AM in encapsulated tablets and will receive full information about their treatment (i.e., high expectation).
- Treatment continuation and high expectation - open continuation (OC):
Patients in this group remain on prescribed AM in identical encapsulated tablets and will receive full information about their treatment (i.e., high expectation).
- Treatment discontinuation and medium expectation - hidden discontinuation (HD):
Patients in this group will receive gradually decreasing doses of prescribed AM in encapsulated tablets and will be informed about a 50% chance of discontinuing versus remaining on AM (i.e., moderate expectation).
- Treatment continuation and medium expectation - hidden continuation (HC):
Patients in this group will remain on prescribed AM in identical encapsulated tablets and will be informed about a 50% chance of discontinuing versus remaining on AM (i.e., moderate expectation).

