2.3 Sample Size

A medium effect size of $f=0.22$, a significance level of $\alpha=0.05$, and a power of 80% were assumed. This resulted in 168 patients needed in total (i.e. 42 per group) using an ANOVA model (with main effects and interactions). Furthermore, with an expected drop-out rate of at most 15%, in total 196 patients need to be recruited (i.e. 49 per group).

Sample size calculation was conducted using G*Power (version 3.1.9.2).

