2.5 Statistical Interim Analyses and Stopping Guidance

No interim analysis is planned.

Criteria for individual study discontinuation will be reviewed during each study visit and, in case of monitoring, during each additional visit. If a participant falls acutely ill (e.g. Covid) during the discontinuation process, a physician may decide to extend the discontinuation process by the duration of the illness (max. 4 weeks). If so, the participant will continue to receive the currently administered dosage of medication from the study team. Measurements will be postponed accordingly and no additional interim measurements will take place. Study participation will be terminated in case of the patient's withdrawal of his/her informed consent, pregnancy, medical or psychological objections by the study physician or psychologist (i.e., severe depressive symptomatology, recurrence, suicidality, other serious or severe AEs, etc.), or insufficient compliance regarding the study participation or the medication. In these cases, the study physician informs about further treatment options and refers to other contact points in an interview. The continuation of the entire study will be questioned by the principal investigator in case of reoccurring AEs that might be causally related to the study treatment regimen, medical or psychological concerns by the study physician or psychologist, no or insufficient study activity (e.g. enrolment rate < 5 per year), or unforeseeable complications that do not justify study continuation. A safety board will monitor the study according to "Guidelines of Good Clinical Practice" (International Conference on Harmonisation of Technical Requirements for Registration of Pharmaceuticals for Human Use, 2015) and will meet regularly. See study protocol for decision path.

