3.1 Confidence Intervals and *P* Values

All applicable statistical tests will be two-sided and will be performed using a 5% significance level. All confidence intervals presented will be 95% and two-sided. Analyses of secondary and safety outcomes will be performed exploratory without adjustment for multiple testing.

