5.1.2 Secondary endpoints

- a) Discontinuation symptom load over the clinical observation period (i.e. assessments from FU1 till FU3 will be considered and cover reported symptoms between week 14 until week 52) assessed by the Discontinuation Emergent Signs and Symptoms Scale (DESS; Rosenbaum et al., 1998):
As for the primary endpoint AUC will be calculated from the measurements of FU1, FU2, and FU3.
- b) Recurrence (yes / no) during experimental phase, i.e., appearance of a new depressive episode after full, sustained remission of depressive symptoms over the experimental period (i.e., assessments from t1 till t9 will be considered and cover reported symptoms between week 1 until week 13). Recurrence will be monitored weekly during run-in and (dis-)continuation phase and biweekly during monitoring phase, based on Beck Depression Inventory II and Montgomery Asberg Depression Rating Scale scores (BDI-II, Hautzinger et al., 2009; Montgomery-Asberg Depression Rating Scale [MADRS+], (Davidson et al., 1986; Schmidtke et al., 1988; Williams & Kobak, 2008). If recurrence is suspected (as indicated by BDI-II score >19 or MADRS score >21 over two study visits), corresponding SCID-5-CV sections will be conducted to (dis-)confirm recurrence (Beesdo-Baum et al., 2018; First et al., 2016).

Binary variable first recurrence of depression during experimental phase of trial (i.e. yes/no) will be given at t9.

- c) First recurrence over the course of the trial, i.e., appearance of a new depressive episode after full, sustained remission of depressive symptoms will be monitored weekly during run-in and (dis-)continuation phase, biweekly during monitoring phase, and at 26, 39, and 52 weeks post-baseline, as determined in a time-to-event analysis. Assessments from t1 till FU3 will be considered and cover reported symptoms between week 1 until week 52 based on Beck Depression Inventory II and Montgomery Asberg Depression Rating Scale scores (BDI-II, Hautzinger et al., 2009; Montgomery-Asberg Depression Rating Scale [MADRS+], (Davidson et al., 1986; Schmidtke et al., 1988; Williams & Kobak, 2008). If recurrence is suspected (as indicated by BDI-II score >19 or MADRS score >21 over two study visits), corresponding SCID-5-CV sections will be conducted to (dis-)confirm recurrence (Beesdo-Baum et al., 2018; First et al., 2016). Calendar week of start of new depressive episode will be examined and recorded.

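### Secondary endpoint b), recurrence to week 13, has no sound way of counting patients who leave before t9 without a confirmed recurrence

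*SAP*

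**What the plan says.** SAP section 5.1.2 defines endpoint b) as a new depressive episode at any time from t1 to t9 and reduces it to one value per patient: "Binary variable first recurrence of depression during experimental phase of trial (i.e. yes/no) will be given at t9". Section 5.3.2 puts that value into a binary logistic model with the two randomised factors, their interaction and the stratification variables.

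For missing data, section 5.2 says: "b) No imputation of missing values will be conducted. The analysis is based on the FAS". Section 3.3.2 lets into the FAS everyone for whom data exist, whatever protocol violations occurred. It does not say what counts as available data for a status that spans 13 weeks.

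Section 2.5 lists among the reasons for ending participation "severe depressive symptomatology, recurrence, suicidality, other serious or severe AEs". Recurrence is therefore itself a reason for leaving, and severe symptoms and suicidality are listed beside it as separate reasons. Under section 5.1.2, the SCID-5-CV interview that confirms or rejects a recurrence is triggered by raised BDI-II or MADRS scores over two visits.

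Section 5.2 itemises multiple imputation as a sensitivity analysis for d) and e), but not for b).

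**The concern.** A recurrence makes a patient's status known on the day it is confirmed. The absence of recurrence through week 13 is known only for a patient followed to t9. A patient who leaves in week 4 without recurrence fits neither category, and a yes/no variable has no place for partial follow-up. The analyst must either set the value to missing and lose the patient, or record a *no* that covers weeks nobody observed.

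Both codings distort the rates, usually in opposite directions. If dropout differs between arms, the distortion carries into the odds ratio. Differential dropout is plausible here. Section 1.2 expects symptom load to differ between arms, and section 5.2 expects some patients to stop because of symptom burden or recurrence. A coding decision that the plan leaves open would then help decide which way the comparison leans.

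**Working it through.** **Inputs.** The SAP states no recurrence rate, power or sample size for b), so this endpoint has no figure of its own to reproduce. The primary-endpoint sample size does reproduce. With f = 0.22, two-sided 5%, 80% power, four groups and one numerator degree of freedom (noncentral F, λ = f²N), the smallest N is 165. Rounded to equal groups this is 168, with power 80.9%. The only dropout figure is an overall one: "with an expected drop-out rate of at most 15%, in total 196 patients need to be recruited (i.e. 49 per group". Since "The allocation ratio is 1:1:1:1 for the four groups", each treatment level (discontinuation or continuation) has 196/2 = 98 patients. All recurrence rates and arm-specific dropout rates below are assumptions.

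**Step 1: exclusion, all recurrences observed.** Let n be the patients at a treatment level, e the recurrences and r the share of non-recurrent patients followed to t9. The reported rate is e / (e + (n − e)r) and the reported odds are e / ((n − e)r). With equal n and e at both levels, the spurious odds ratio is the inverse ratio of the two retention shares.

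Take e = 10 and n = 98 at both levels (true rate 10/98 = 10.2%), with 20% against 5% dropout among the 88 non-recurrent patients:
- 20% dropout: 10 / (10 + 88 × 0.80) = 10/80.4 = 12.4%
- 5% dropout: 10 / (10 + 88 × 0.95) = 10/93.6 = 10.7%
- odds ratio: 0.95/0.80 = 1.19, where the truth is 1.00

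Here *no* coding would give the correct 10.2% at both levels, because by construction no leaver recurs.

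**Step 2: both codings, leavers can recur after leaving.** Let recurrence and dropout be independent exponential times over the 12 weeks from t1 to t9, with true risk p and dropout d. Write L = −ln(1 − p) and M = −ln(1 − d). Then:
- P(recurrence seen) = L/(L + M) × [1 − (1 − p)(1 − d)]
- P(recurrence-free completer) = (1 − p)(1 − d)
- exclusion reports seen / (seen + completer); *no* coding reports seen

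With p = 0.20 in both arms, L = 0.2231:
- d = 0.05: M = 0.0513, completer = 0.76, seen = 0.8131 × 0.24 = 0.1951. Exclusion 20.4%, *no* coding 19.5%.
- d = 0.25: M = 0.2877, completer = 0.60, seen = 0.4368 × 0.40 = 0.1747. Exclusion 22.6%, *no* coding 17.5%.
- odds ratio, exclusion: (0.1747/0.60) / (0.1951/0.76) = 1.13
- odds ratio, *no* coding: (0.1747/0.8253) / (0.1951/0.8049) = 0.87

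**Step 3: range.** For equal true risks from 5% to 30%:

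| Dropout | Odds ratio, exclusion | Odds ratio, *no* coding |
|---|---|---|
| 15% vs 15% | 1.00 | 1.00 |
| 5% vs 15% | about 1.06 | 0.93 to 0.95 |
| 5% vs 25% | 1.13 to 1.14 | 0.86 to 0.89 |

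Equal dropout leaves the null odds ratio intact but not the rates: at 15% in every arm, a true 20% reads 21.4% or 18.5%. With a real effect of 10% against 20% (odds ratio 2.25) and dropout of 5% against 25%, the same data give 2.55 under exclusion and 1.96 under *no* coding.

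**Step 4: leavers at higher risk.** In a simulation with a 15% base risk, 25% leavers and three times the recurrence hazard among them, the true rate is 20.9%. Exclusion reads 20.5% and *no* coding 16.5%. The upward bias of exclusion has gone and is slightly reversed. A simple count shows the same: if 4 of 98 patients leave for severe symptoms and are true recurrences, 14/98 = 14.3% is reported as 10/94 = 10.6% under exclusion.

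**The case against.** A reader might infer that the plan drops every patient who leaves early without recurrence. The documents do not support that. Section 5.2 says only that values are not imputed, the FAS wording would also admit a leaver who attended some visits, and a status given at t9 may simply be derived then. This objection stands, so the point does not rest on exclusion. It does not rescue the plan, because the alternative coding is also biased.

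A reader might also infer that the odds ratio is inflated. No direction can be claimed: it depends on the coding, on which arm loses more patients and on the leavers' risk. Nor does the SAP say that patients stopped for severe symptoms leave without a SCID-5-CV interview. That they may go unclassified is an inference.

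On mitigation, section 5.2 has a general sentence treating imputed-data results as sensitivity analyses for the remaining secondary endpoints, and section 5.4 allows further ones. But the first only ranks results and the second is permissive, so neither commits to imputing b). Sections 4.4 and 5.3 would make differential dropout visible through withdrawal reasons and missing counts by group, without showing its effect on the estimate. Endpoint c) follows the same event from t1 by Cox regression, but it estimates a hazard ratio over 52 weeks with censoring at treatment switching, not the 13-week risk. Finally, b) is exploratory under section 2.4, which limits the stakes.

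**Conclusion.** The concern holds in this form: a yes/no status, no imputation and logistic regression cannot correctly handle patients who leave before t9 without a confirmed recurrence, and neither coding the plan permits gives a sound 13-week comparison when dropout differs. The effect is modest. At equal true risks, the null odds ratio moves by about 6% for a 10-point dropout gap and by about 13% for a 20-point gap, in opposite directions under the two codings. These figures rest on assumed recurrence and dropout rates, and all but the higher-risk case in Step 4 assume that dropout is independent of recurrence. For an exploratory secondary endpoint this should be corrected, but it does not threaten the trial's main conclusion.

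**What to change.** Estimate b) from the dated recurrences already recorded for c), truncated at t9: a Kaplan-Meier 13-week risk by group, with a Cox or complementary log-log model holding the same factors and stratification variables. Leavers then contribute up to their last visit. Under the independent-dropout assumption of Step 2, this returns 20% in both arms. State whether c)'s censoring at treatment switching also applies, since b) as written uses FAS data regardless of protocol violations.

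Censoring alone is not enough, because it assumes leavers carry the same risk as those who stay. Extend the 20-fold imputation of section 5.2 to b) as a committed sensitivity analysis, with BDI-II and MADRS scores up to the last visit as predictors.

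The cost is SAP wording and some programming, with no new data. The effect measure changes from an odds ratio to a hazard ratio or risk difference, unless the logistic model is kept on the imputed data.

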3.3.2 Full analysis set (FAS)

For all secondary endpoints the full analysis set is used. FAS is as complete as possible and as close as possible to the ITT population. All available data will be used and all patients with available data will be included as belonging to their randomization arm, regardless of whether they refused therapy, or whether other protocol violations are known.

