4.4 Withdrawal / Follow-up

Information on the number and level of withdrawals/drop outs, number included in the analysis and the number died will be presented in CONSORT diagram format with numbers and reasons for withdrawal and/or exclusion from analysis given at each visit. Levels of withdrawal are defined as:

- Patient withdraws from treatment, but not from the study, and continues to participate in study visits
- Patient withdraws from study, but all data collected up to date withdrawal can be kept and analyzed
- Patient withdraws from study and withdraws all data

Individual missed assessment time points do not automatically lead to withdrawal from the study.

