5.4 Sensitivity Analyses

In case of a violation of the normality assumption of the residuals, the primary analysis will be repeated with log transformed dependent variable, where appropriate.

Results of the post-hoc group comparisons will then be presented as adjusted mean factors with corresponding 95%- Wald confidence intervals (resulting from back-transformation of the adjusted mean differences) and p-values will be given.

The primary endpoint and the secondary endpoint a) will additionally be analyzed using the complete case data only, without adjustment for baseline discontinuation symptoms, and in the per protocol population.

Further sensitivity analyses on imputed data might be performed, see Section 5.2 for details. All endpoints might be analysed in the per protocol population.

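### Time to first recurrence is censored at treatment switch, which does not fit the FAS rule that governs it, and no Cox model keeping post-switch follow-up is fixed

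*SAP*

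**What the plan says.** SAP section 5.2, item c) for the secondary endpoints, reads "Patient observations will be censored at the time point where treatment switching is observed, i.e". It then names two kinds of switch: "treatment discontinuation if treatment should be continued", and the reverse, taking medication in an arm assigned to stop. Other missing data for c) are not imputed.

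The population rule is in section 3.3.2: "For all secondary endpoints the full analysis set is used". The FAS is then described: "All available data will be used and all patients with available data will be included as belonging to their randomization arm", and the sentence goes on to keep patients who declined therapy or violated the protocol. Section 5.2 repeats the assignment. After setting the primary endpoint and endpoint a) apart, it says "For all other secondary endpoints the analysis based on the FAS will be primarily reported". Endpoint c) is among these.

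Section 5.3.2 gives one Cox model for c), with the two factors, their interaction and the stratification variables, and does not mention switching. In section 5.4 the firm sensitivity analyses cover only the primary endpoint and a). For c) there is only an option: "All endpoints might be analysed in the per protocol population".

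**The concern.** Censoring at switch removes follow-up because the patient departed from the assigned treatment, and the FAS definition says that such departures do not matter. Switchers stay in the set, but their later data do not. The result would still be reported as an FAS analysis.

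Such later data can exist. Section 4.4 foresees this level of withdrawal: "Patient withdraws from treatment, but not from the study, and continues to participate in study visits". A recurrence seen at such visits would be recorded and then left out of the model.

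The Cox model needs censoring to be unrelated to the coming event, given the covariates. Section 5.2, in its rule for the primary endpoint, links the end of study treatment to symptoms: "In case of individual termination of study treatment (due to burden of discontinuation symptoms or recurrence". That sentence concerns ending study treatment, not restarting medication in weeks 14 to 52. That a restart may follow worsening mood is therefore an inference. It is a plausible one, because section 5.1.2 requires raised scores over two visits and then an interview before a recurrence is confirmed, so a restart can come first.

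**Working it through.** **1. The rules side by side**

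| Question | FAS rule (3.3.2, and 5.2 for c) | Censoring rule (5.2, item c) |
|---|---|---|
| Who is analysed? | All with data, as randomised | The same patients |
| Data after departure from treatment? | Used | Dropped from the switch onward |

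The conflict is in the second row only.

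**2. Which recurrence analyses keep post-switch data?** Endpoint b), recurrence yes/no in weeks 1 to 13, has no switch-censoring. Endpoint c), weeks 1 to 52, has it. The optional per-protocol analysis excludes patients with major deviations, so it moves further from the comparison as randomised. For weeks 14 to 52 no as-randomised recurrence analysis is fixed.

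**3. Size.** The SAP states no recurrence rate, hazard ratio (HR), event count or switching rate for c), so there is no figure to reproduce. The sample size in section 2.3 concerns the primary endpoint. Every rate below is an assumption.

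The check is a simulation with exponential recurrence times, 6,000 patients per level of the treatment factor and 52 weeks. Recurrence on assigned treatment is 50% (discontinuation) against 35% (continuation), with 40% against 20% in brackets. The HRs implied without switching are ln(0.50)/ln(0.65) = 1.61 and ln(0.60)/ln(0.80) = 2.29. Restart occurs 0 to 4 weeks before the recurrence and averts half of those recurrences. Continuation patients who stop do so at weeks 13 to 39 and then carry the discontinuation hazard. Events are scaled to 196 patients.

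| Scenario | HR as randomised | HR switch-censored | Events, as randomised / switch-censored |
|---|---|---|---|
| No switching | 1.60 (2.35) | 1.60 (2.35) | 83/83 (59/59) |
| Half of continuation patients stop | 1.40 (1.70) | 1.58 (2.14) | 88/76 (65/55) |
| Restart before 25% of recurrences | 1.29 (1.88) | 1.16 (1.70) | 78/72 (54/49) |
| Restart before 50% of recurrences | 1.11 (1.58) | 0.82 (1.17) | 72/60 (49/40) |
| Half stop, and 25% restart | 1.20 (1.49) | 1.20 (1.70) | 82/64 (59/45) |

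Simulation error on each HR is roughly 5% to 9%.

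As a check, if a share p of recurrences is preceded by restart, the switch-censored HR is about HR × (1 − p). This gives 1.61 × 0.75 = 1.21 and 1.61 × 0.50 = 0.80, against 1.16 and 0.82 simulated.

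**4. Reading.** Restart before recurrence pulls the switch-censored HR below the no-switching value. Stopping in the continuation arms, if unrelated to prognosis, leaves it near that value (1.58 against 1.60) and lowers the as-randomised HR (1.40). With both at once the two models can agree by coincidence (1.20 and 1.20). The direction of the difference is not predictable in advance.

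**The case against.** The strongest reply is that section 3.3.2 defines a patient set, while section 5.2 gives a specific censoring rule that any analyst would follow. Switchers remain in the FAS in their own arm until they switch, and the rule suits the aim in section 1.2 of separating drug from expectation effects. On this view a second Cox model for an exploratory endpoint is only a preference. Part of this stands: the rule is clear enough to run, and the target is defensible. But the SAP does not name that target, the FAS text speaks of all available data and not only of patients, and no other view of weeks 14 to 52 is fixed.

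Three further objections limit the point.

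- **Section 2.5** ends participation for recurrence, severe depressive symptoms or insufficient medication compliance, so some switchers will have no later data. No model recovers those.
- **Onset dating.** Section 5.1.2 records the week in which an episode began, so a recurrence with onset before a restart may still count. With a true HR of 2.0 and a share d recovered in this way, the switch-censored HR is about 2 × (1 − p(1 − d)). At p = 40% this is 1.2, 1.6 and 2.0 for d = 0, 0.5 and 1.
- **Precision.** With an assumed 70 events evenly spread, the 95% limits are a factor of exp(1.96 × 2/√70) = 1.60 either side for a main effect, and exp(1.96 × 4/√70) = 2.55 for the interaction. Small shifts would not be visible.

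A reader might infer that the plan will understate recurrence after discontinuation. The SAP does not support this: it gives no restart reasons or rates, and the table shows differences both ways. Nor does distortion of the interaction follow, since that needs unequal restart in the open and hidden discontinuation arms. A reader might also infer that stopping under the discontinuation plan for the continuation groups (Table 1) will be censored as a switch. The SAP does not say so, the timing in Table 1 is not clear in the text available here, and the protocol may settle it.

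**Conclusion.** The point holds as a minor one. The switch-censoring of endpoint c) does not fit the FAS rule that the SAP applies to it, and it is the only fixed analysis of recurrence beyond week 13. It is biased if switching is related to impending recurrence, which is plausible but not shown. Its size cannot be stated from the SAP. The HRs above show direction and order of size under assumed recurrence, stopping and restart rates and are not predictions. How planned stopping in the continuation groups is coded is a matter for clarification, not an error. Section 2.4 makes all secondary endpoints exploratory, so the primary analysis and the sample size are unaffected.

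**What to change.** 1. Reconcile sections 3.3.2 and 5.2, for example by stating in the FAS definition that endpoint c) has two analyses and which of them uses all follow-up.
2. Fix in advance a Cox model for c) on the FAS as randomised, using all available follow-up without censoring at switch (treatment policy). Report it beside the switch-censored model (while on assigned treatment), each labelled with its estimand.
3. Tabulate switches by arm, reason and week. Section 4.4 already reports withdrawals with reasons at each visit, so this mainly adds restarts and later stops.
4. As a clarification, state how stopping under the Table 1 discontinuation plan for the continuation groups is coded in this analysis.

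The cost is a few sentences, one extra model fit and one table, on data already collected. The as-randomised model answers a different question: it does not correct the switch-censored HR, and it is itself attenuated if switching alters the risk of recurrence (1.40 against 1.60 in the stopping scenario). This is why both should be reported.
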